## 6. STUDY TREATMENT

Combination treatment with INCB099280 and axitinib will be administered orally BID on a continuous daily dosing schedule (ie, without a break in dosing in the absence of drug-related toxicity). Study treatment will be administered in consecutive 21-day cycles as long as participants are receiving benefit and have not met any criteria for study withdrawal. INCB099280 may be administered for up to 2 years (up to 35 cycles).

If a participant is unable to tolerate combination treatment, they will have met the criterion for study treatment discontinuation. However, on a case-by-case basis, after discussion between the medical monitor and the investigator, a decision may be made to continue INCB099280 monotherapy.

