**Table 10: Non-Immune-Related Adverse Event Management Guidelines for INCB099280**

CTCAE Grade	Suggested Modification for INCB099280
Grade 1 or Grade 2	Continue treatment at the discretion of the investigator.
Grade 3	Withhold treatment until resolution to $\leq$ Grade 1 or baseline. Restart INCB099280 at the same dose at the discretion of the investigator. Permanently discontinue study drug at the third occurrence unless approved by the medical monitor to continue.
Grade 4	Permanently discontinue study treatment or discuss with the medical monitor if a treatment algorithm for CTCAE Grade 3 events (above) is appropriate.

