**Table 11: Management Guidelines for Immune-Related Adverse Events (Continued)**

Severity (CTCAE v5 Grade)	INCB099280	Evaluation and Management
Diarrhea/colitis (continued)		
Grade 2 or Grade 3	Withhold INCB099280 until improvement to ≤ Grade 1.	
Grade 2:
 
 
Consider consultation with a gastroenterology specialist.
 
Consider symptomatic treatment with an antidiarrheal agent if infection has been ruled out.
 
Administer systemic corticosteroids (prednisone 1 mg/kg or equivalent) until symptoms improve to Grade 1 and then taper over 4-6 weeks.
 
Consider infliximab or vedolizumab for steroid-refractory colitis (no decrease by 1 grade in 72 hours) or steroid-dependent colitis or colitis with high-risk features on initial endoscopy examination.
 
 
Grade 3:
 
 
Administer systemic corticosteroids (prednisone 1-2 mg/kg or equivalent) until symptoms improve to Grade 1 and then taper over 4-6 weeks.
 
Consider IV methylprednisolone.
 
Consider early introduction of infliximab or vedolizumab in addition to steroids in participants with high-risk endoscopic features or inadequate response to steroids.
 
Consider hospitalization for participants with dehydration or electrolyte imbalance.
 
Consultation with a gastroenterology specialist for additional workup as appropriate.
 

Grade 4 or recurrent Grade 3	Permanently discontinue INCB099280.	
 
Administer IV methylprednisolone 1-2 mg/kg or equivalent until symptoms resolve to Grade 1 and then taper over 4-6 weeks.
 
If no improvement after 3 days, consider infliximab or vedolizumab.
 
Consultation with a gastroenterology specialist for additional workup as appropriate.
 

Hepatitis (AST/ALT increased and/or total bilirubin increased)		
Grade 1	Continue INCB099280.	
 
Repeat laboratory measurements 1-2 times/week.
 
Consider alternate etiologies.
 
Provide supportive care for symptoms.
 

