**Table 12: Axitinib Toxicity Management Guidelines (Continued)**

Event/Severity (CTCAE v5 Grade)	Management Guideline
Cardiac failure	
Asymptomatic cardiomyopathy (LVEF > 20% but < 50% below baseline or below the lower limit of normal of baseline was not obtained)	
 
Interrupt axitinib until resolution to Grade 0 or 1 or baseline.
 
Resume axitinib with a dose reduction of 1 level (see Table 9).
 

Clinically manifested CHF	Discontinue axitinib.
Fistula	
Trachea-esophageal fistula Any grade	Discontinue axitinib.
Fistula other than trachea-esophageal Grade 1 or Grade 2	
 
Interrupt axitinib.
 
Either resume axitinib at a dose reduction (see Table 9) or discontinue depending on the severity and persistence of the adverse reaction.
 

Fistula other than trachea-esophageal fistula Grade 3 or Grade 4	Discontinue axitinib.
Impaired wound healing	
Any grade	
 
The safety of resumption of axitinib after resolution of wound healing has not been established.
 
Either resume axitinib at a reduced dose (see Table 9) or discontinue, depending on the severity and persistence of the adverse reaction.
 

GI perforation	
Any grade	Discontinue axitinib.
Arterial thromboembolic events	
Any grade	Discontinue axitinib.
Venous thromboembolic events	
Any grade	
 
Interrupt axitinib.
 
Either resume axitinib at the same dose level or discontinue, depending on the severity of the VTE.
 
Permanently discontinue for severe VTE.
 

Hemorrhage	
Grade 1	
 
For hemoptysis, interrupt axitinib and evaluate underlying causes.
 
Resume axitinib at the discretion of the investigator.
 
For other Grade 1 hemorrhage/bleeding events, continue axitinib at the current dose level and monitor as clinically indicated.
 

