**Table 13: Management Guidelines for Specific Adverse Events Common to Both INCB099280 and Axitinib**

Event/Severity (CTCAE v5 Grade)	Evaluation and Management
Liver enzyme elevationa	
ALT/AST ≥ 3 × ULN but < 10 × ULN without concurrent total bilirubin ≥ 2 × ULN	
 
Interrupt both INCB099280 and axitinib until resolution to Grade 0-1.
 
Consider rechallenge with INCB099280 and axitinib.
 
 
See Table 14 for further details on event management.

ALT/AST ≥ 3 × ULN with concurrent total bilirubin ≥ 2 × ULN or ALT/AST ≥ 10 × ULN	Permanently discontinue both INCB099280 and axitinib.
Diarrhea	
Grade 1 or Grade 2	Initiate symptomatic medications. See Table 11 for further details on event management.
Grade 3	
 
Interrupt axitinib and initiate symptomatic medications.
 
If diarrhea is controlled, axitinib may be resumed at either the same dose level or reduced by 1 dose level (see Table 9).
 
 
See Table 11 for further details on event management.

Grade 4	Interrupt axitinib until resolution to Grade < 2, then restart axitinib dose reduced by 1 dose level (see Table 9 ). See Table 11 for further details on event management.
Major adverse cardiovascular events	
Grade 3 and Grade 4	Permanently discontinue both INCB099280 and axitinib.

a Consider corticosteroid therapy.

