### 6.6.7. Criteria for Permanent Discontinuation of Study Drugs Due to Unacceptable Toxicity

Unacceptable toxicity or the inability to tolerate study treatment with both INCB099280 and axitinib will require discontinuation of study treatment.

On a case-by-case basis, following discussion between the medical monitor and investigator, participants who are required to discontinue treatment with axitinib may continue treatment with INCB099280 until such time that an INCB099280 discontinuation criterion is met.

Study treatment must be permanently discontinued for the following:

- Any AE meeting a criterion for treatment discontinuation of INCB099280 and axitinib as detailed in [Table 11](#), [Table 12](#), [Table 13](#), and [Table 14](#).
- AEs requiring more than the allowed dose reductions of axitinib as detailed in [Table 9](#).
- A persistent AE requiring an interruption of study treatment for more than 3 weeks (21 days) unless a greater delay has been approved by the sponsor.
- The occurrence of an AE that is related to study drug that, in the judgment of the investigator or the sponsor's medical monitor, compromises the participant's ability to continue study-specific procedures or is considered to not be in the participant's best interest.

See Section [7](#) for discontinuation procedures.

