## **7. DISCONTINUATION OF STUDY TREATMENT AND PARTICIPANT WITHDRAWAL**

### **7.1. Discontinuation of Study Treatment**

#### **7.1.1. Reasons for Discontinuation**

Participants **must** be discontinued from study treatment for the following reasons:

- Radiographically confirmed disease progression.

Note: In select instances, participants may continue on treatment past confirmed disease progression. See Section 6.6.8 for details.

- Consent is withdrawn.

Note: Consent withdrawn means that the participant has explicitly indicated that they do not want to be followed any longer; in this case no further data, except data in the public domain, may be solicited from or collected on the participant. Consent may also be partial. Participants may choose to discontinue study treatment and remain in the study to be followed for disease status follow-up.

- Further participation would be injurious to the participant's health or well-being, in the investigator's medical judgment.
- Unacceptable toxicity as noted in Section 6.6.7.
- The study is terminated by the sponsor or the DMC.
- The study is terminated by the local health authority, IRB, or IEC.
- The participant has completed 2 years of study treatment with INCB099280 from the date of first dose, including dose interruptions.

Note: If a participant is unable to tolerate combination treatment, they will have met the criterion for study treatment discontinuation. However, on a case-by-case basis, after discussion between the medical monitor and the investigator, a decision may be made to continue INCB099280 monotherapy for a maximum of 2 years.

A participant **may** be discontinued from study treatment as follows:

- The participant is found not to have met eligibility criteria.
- If a participant is noncompliant with study procedures or study drug administration in the investigator's opinion, the sponsor should be consulted for instruction on handling the participant.

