### 8.3.6. Echocardiograms

Left ventricular systolic function as measured by LVEF will be assessed by echocardiography at screening and as clinically indicated. Every effort should be made to schedule serial monitoring at the same cardiac imaging facility.

Participants should be assessed and monitored for the development of symptoms and signs of CHF. Participants who develop CHF should permanently discontinue study treatment.

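### The toxicity tables and the body text conflict on whether permanently stopping one study drug also stops the other

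*Protocol*

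**What the plan says.** **General rule.** Section 7.1.1 states: "If a participant is unable to tolerate combination treatment, they will have met the criterion for study treatment discontinuation". Section 1 (Treatment Groups and Duration), Section 4.1 and Section 6 say the same. The exception follows directly: case by case, after the medical monitor and investigator confer, "a decision may be made to continue INCB099280 monotherapy". Section 6.6.7 repeats the exception in the same direction: "participants who are required to discontinue treatment with axitinib may continue treatment with INCB099280 until such time" as an INCB099280 stopping criterion is met. It has no mirror rule for axitinib.

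**Diarrhea.** For Grade 4, Table 13 (events common to both drugs) interrupts axitinib until Grade < 2, "then restart axitinib dose reduced by 1 dose level", and points to Table 11. For Grade 4 or recurrent Grade 3 diarrhea/colitis, Table 11 says "Permanently discontinue INCB099280".

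**Creatinine.** For Grade 3 or 4, Table 12 interrupts axitinib, resumes it one level lower after recovery, and points to Table 11. Table 11 permanently stops INCB099280 at those grades if it is directly implicated in the renal toxicity.

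**CHF.** For clinically manifested CHF, Table 12 says "Discontinue axitinib". Section 8.3.6 says "Participants who develop CHF should permanently discontinue study treatment". Section 6.6.6.2 requires permanent discontinuation of study drug without saying which one, and refers back to Table 12.

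**The concern.** The protocol sets out to evaluate the combination and makes intolerance of it a reason to stop study treatment. A toxicity row that restarts axitinib while the row it cites permanently stops INCB099280 leads to a regimen that the body text does not provide for. In CHF the gap runs the other way: one route leaves continuation of INCB099280 open and another closes it.

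Two sites that each follow a protocol passage could then treat the same participant differently. This is first a matter of participant safety. It also affects the data. TEAEs leading to interruption, reduction or permanent discontinuation of either drug are a primary endpoint in Part 1 and a secondary endpoint in Part 2. Section 10.4.2.1 runs the TEAE window to 90 days after the last dose of study treatment, or to new anticancer therapy if earlier. Whether the second drug continues therefore changes exposure, treatment duration and the period over which events are collected.

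**Working it through.** The plan gives no figure to reproduce here. The check is a side-by-side reading.

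| Event | Axitinib | INCB099280 | Result if both are followed |
|---|---|---|---|
| Grade 4 diarrhea | Table 13: interrupt, restart one level lower | Table 11: permanent stop | Axitinib alone |
| Recurrent Grade 3 diarrhea | Table 13: interrupt, may resume at the same or a lower level if controlled | Table 11: permanent stop | Axitinib alone possible |
| Grade 3 or 4 creatinine increase, INCB099280 directly implicated | Table 12: interrupt, resume one level lower | Table 11: permanent stop | Axitinib alone |
| Clinically manifested CHF | Table 12: stop | Table 12 silent; Section 6.6.7 could allow continuation; Section 8.3.6 stops study treatment | INCB099280 alone, or nothing |

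**Is axitinib alone provided for anywhere?** Sections 1, 4.1, 6, 6.6.7 and 7.1.1 name only INCB099280 as continuing monotherapy. Table 14 (Scenario 2) gives axitinib first for 2-3 weeks, but as a staged step toward resuming INCB099280, not after its permanent stop. Section 6.6.1 lets the two drugs be handled independently for interruptions and says nothing similar about permanent discontinuation.

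**Does Section 6.6.7 settle it?** It requires study treatment to stop for any AE meeting a discontinuation criterion for INCB099280 and axitinib in Tables 11 to 14. That can mean a criterion for both drugs or for either. On the either-drug reading the axitinib restart could not follow a permanent INCB099280 stop. On the both-drugs reading the question stays open.

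**Could Table 13 simply be written one drug at a time?** Its liver-enzyme row (the more severe category) and its major-cardiovascular-event row state that both drugs stop. The diarrhea rows give an axitinib action and a pointer, so they do not say what happens to axitinib once INCB099280 has stopped for good.

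**What changes in the counts?**
- Diarrhea and creatinine: INCB099280 is permanently stopped whichever way axitinib is handled, so the participant already counts as having discontinued either drug. What can differ is whether axitinib is recorded as reduced or as discontinued.
- CHF: axitinib stops under every reading, so the participant again counts. What can differ is the INCB099280-specific discontinuation.

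**The case against.** The strongest case against is that the general rule already answers the axitinib-alone question. Table 11 covers immune-related events. If the diarrhea is not immune-related, Table 10 applies: "Permanently discontinue study treatment or discuss with the medical monitor if a treatment algorithm for CTCAE Grade 3 events (above) is appropriate". Through its second branch INCB099280 can restart, and Table 13's axitinib restart then fits a continuing combination. Section 6.6 also asks for the most conservative recommendation when attribution is difficult, and it names diarrhea as difficult. On this view Table 13 lacks only a cross-reference.

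Part of this stands. The diarrhea conflict arises when the event is managed under both Table 13 and Table 11, and a first Grade 3 event shows no conflict. But Table 13 sends the reader to Table 11 itself, and its restart carries no condition that INCB099280 also continues. Table 10's first branch stops study treatment, which does not match that restart either. The conservative rule addresses unclear attribution, not whether axitinib may continue alone.

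On CHF, Table 12 is an axitinib table, so its silence is not permission to continue INCB099280, and Section 8.3.6 can be read as the criterion that ends INCB099280 under Section 6.6.7. That reading is reasonable, but the reader has to construct it, and Section 6.6.6.2 directs the reader to Table 12, where only axitinib is named.

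Three stronger inferences are tempting and are not supported:
- **That the participant-level endpoint is corrupted.** Discontinuation of either drug is counted under every reading. Only drug-specific counts, exposure and duration move.
- **That about 26 participants are affected.** Section 2.3.2 reports, for axitinib plus pembrolizumab, discontinuation of either drug in 30.5% and of both in 10.7%. The difference is 30.5% − 10.7% = 19.8%, and 0.198 × 132 ≈ 26. That difference covers everyone who stopped only one drug for any AE, including those who stopped only axitinib, for whom this protocol has a rule. The 9.1% for Grade 3 or 4 diarrhea in the same section includes first Grade 3 events. Neither figure measures the rows in conflict.
- **That an ORR analysis excluding responses on a single agent is required.** Table 22 places anyone given at least one dose of either treatment in the full analysis set (FAS), and Section 10.3 calls the study exploratory with no formal tests. How to count such responses is a choice of estimand, not an error to correct.

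**Conclusion.** The conflict is real and should be corrected. Followed together, Tables 11 and 13 (Grade 4 diarrhea) and Tables 11 and 12 (Grade 3 or 4 creatinine increase with INCB099280 directly implicated) lead to axitinib alone, which no passage provides for as continuing treatment. Recurrent Grade 3 diarrhea can lead there too. For CHF, Table 12, Section 6.6.6.2, Section 6.6.7 and Section 8.3.6 do not agree on which drug or drugs stop.

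The effect is divergent handling of identical participants, with differences in exposure, in drug-specific reduction and discontinuation counts, and in treatment duration. The protocol gives no rate for Grade 4 diarrhea, recurrent Grade 3 diarrhea, INCB099280-implicated creatinine increase or CHF under this combination, so the size cannot be put as a number of participants. The conclusion rests on the text alone and assumes that the diarrhea event is managed under both tables, as Table 13's own pointer directs.

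**What to change.** 1. Reconcile the diarrhea rows of Table 13 and the creatinine row of Table 12 with Table 11 and Sections 6, 6.6.7 and 7.1.1. State in each place whether axitinib may continue once INCB099280 is permanently stopped.
2. Reconcile the CHF row of Table 12 with Sections 6.6.6.2, 6.6.7 and 8.3.6, naming the drug or drugs that stop in place of a general term.
3. In the Section 6.6.7 list, say whether the criterion that refers to Tables 11 to 14 means both drugs or either drug.

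The clinical team decides which rule stands; this review proposes none. The cost is a wording amendment to a few table rows and sections, with no change to sample size, data collection or planned analyses.

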**Table 14: Algorithms of Decision on INCB099280/Axitinib Rechallenge After Recovery From Drug-Related ALT/AST Elevation**

Initial ALT/AST Elevation Scenario	Rechallenge Decision
Scenario 1: ALT/AST $> 3 \times \text{ULN}$ concurrent with total bilirubin $\geq 2 \times \text{ULN}$ (excluding biliary obstruction) and/or PT/INR $> 1.5 \times \text{ULN}$ (ie, ALT/AST elevation with clinically significant signs of hepatic dysfunction)	No rechallenge with either INCB099280 or axitinib is allowed.
Scenario 2: ALT/AST $> 3\text{-}5 \times \text{ULN}$ without clinically significant signs of hepatic dysfunction (ie, total bilirubin $< 2 \times \text{ULN}$ and PT/INR $< 1.5 \times \text{ULN}$ )	
Unacceptable toxicity or the inability to tolerate study treatment with both INCB099280 and axitinib will require discontinuation from both study drugs.
 
Combination treatment with INCB099280 and axitinib can be resumed sequentially with axitinib (at the previous dose) resumed first for 2-3 weeks with weekly liver test monitoring:
 
 
• If no recurrence, rechallenge with INCB099280.
 
• If ALT/AST recurrence is <math>> 5 \times \text{ULN}</math> (ie, Grade 3 or 4), discontinue axitinib. A rechallenge with INCB099280 monotherapy may be considered on a case-by-case basis after discussion between the medical monitor and investigator. See Section 6.6.7 for further details.
 
• If ALT/AST recurrence is <math>> 3\text{-}5 \times \text{ULN}</math> (ie, Grade 2), reduce the dose of axitinib and then rechallenge or discontinue axitinib and rechallenge with INCB099280. If axitinib needs to be discontinued, on a case-by-case basis, after discussion between the medical monitor and investigator, INCB099280 monotherapy may be considered.
 
 
Permanently discontinue INCB099280 if ALT/AST recurrence is <math>> 5 \times \text{ULN}</math> or interrupt INCB099280 if ALT/AST recurrence is <math>> 3</math> to <math>5 \times \text{ULN}</math> after rechallenge.

Scenario 3: ALT/AST $> 5$ to $10 \times \text{ULN}$ without clinically significant signs of hepatic dysfunction (ie, total bilirubin $< 2 \times \text{ULN}$ and PT/INR $< 1.5 \times \text{ULN}$ ).	No rechallenge with either INCB099280 or axitinib is allowed.
Scenario 4: ALT/AST $> 10 \times \text{ULN}$ without clinically significant signs of hepatic dysfunction	No rechallenge with either INCB099280 or axitinib is allowed.

Note 1: Participants should have weekly monitoring with liver tests (ie, liver enzyme and function tests) for 2-3 weeks after each drug rechallenge.

Note 2: If both study drugs are discontinued due to a hepatic event, participants should be monitored until AE resolution as per Protocol and continue imaging as per Protocol.

Note 3: Liver tests include liver enzyme (ALT, AST, and ALP) and liver function (bilirubin and PT/INR) tests.

### 6.6.7. Criteria for Permanent Discontinuation of Study Drugs Due to Unacceptable Toxicity

Unacceptable toxicity or the inability to tolerate study treatment with both INCB099280 and axitinib will require discontinuation of study treatment.

On a case-by-case basis, following discussion between the medical monitor and investigator, participants who are required to discontinue treatment with axitinib may continue treatment with INCB099280 until such time that an INCB099280 discontinuation criterion is met.

Study treatment must be permanently discontinued for the following:

- Any AE meeting a criterion for treatment discontinuation of INCB099280 and axitinib as detailed in [Table 11](#), [Table 12](#), [Table 13](#), and [Table 14](#).
- AEs requiring more than the allowed dose reductions of axitinib as detailed in [Table 9](#).
- A persistent AE requiring an interruption of study treatment for more than 3 weeks (21 days) unless a greater delay has been approved by the sponsor.
- The occurrence of an AE that is related to study drug that, in the judgment of the investigator or the sponsor's medical monitor, compromises the participant's ability to continue study-specific procedures or is considered to not be in the participant's best interest.

See Section [7](#) for discontinuation procedures.

#### **6.6.8. Treatment After Initial Evidence of Radiologic Evidence of Disease Progression**

An immunotherapeutic agent such as INCB099280 may produce antitumor effects by potentiating endogenous cancer-specific immune responses. The response patterns seen with such an approach may extend beyond the typical time course of responses seen with cytotoxic agents and can manifest as a clinical response after an initial increase in tumor burden or even the appearance of new lesions. Principles of iRECIST ([Seymour et al 2017](#)) may be used by the investigator to guide treatment decisions once an initial RECIST v1.1 progression is noted.

If radiologic imaging shows PD, tumor assessment should be repeated after  $\geq 4$  weeks but no later than 8 weeks to confirm PD with the option of continuing treatment per [Table 15](#) while awaiting radiologic confirmation of progression. When feasible, participants should not be discontinued from study treatment until PD is confirmed; however, the decision to continue study treatment after the first evidence of PD is at the investigator's discretion based on the clinical status of the participant. Participants must have the opportunity to be reconsented if treatment beyond initial RECIST v1.1 progression is planned.

Participants may receive study treatment while waiting for confirmation of PD if they are clinically stable, as defined by the following criteria:

- Absence of signs and symptoms (including worsening of laboratory values) indicating PD.
- No decline in ECOG performance status.
- Absence of rapid PD.
- Absence of progressive tumor at critical anatomical sites (eg, cord compression) requiring urgent alternative medical intervention.

